9.5 PHASE 5: STUDY EXIT

Subjects will be determined exited from the study when they complete the questionnaires for each required follow up or are determined as exited if a circumstance removes them for a specific reason earlier than planned. Subjects meeting the study requirements as planned will be exited from the study after the 36 month follow-up data collection. If a subject reaches the 36 month follow-up point and is experiencing new or ongoing adverse event, the study sponsor and treating investigator should be contacted to discuss the need and/or methods for continued surveillance of the event.

Subjects that completed the 24-month follow-up and exited per protocol version D will be invited to continue participation in the study through their 36 month post Vivaer procedure date. Subjects who elect to continue with the study will be asked to re-consent for their participation through 36 months. Subjects that decline 36-month follow-up participation or re-consent, will be exited from the study after their 24 month follow-up data collection. Reasons for declining participation in the 36 month extension will be recorded in the eCRF.

9.6 STUDY ASSESSMENTS

The following study assessments will be collected at the specific time-points mentioned in the above phases.

Visual Assessment of Treatment Area (Nasal Evaluation): The treated area within each nostril will be visually assessed. The use of an endoscope for visual assessment is required. For consistency in reporting across sites, a study CRF will outline specific observations to be assessed. In addition, representative still photographs of each nostril will be captured at each visit

The following assessments will be obtained from the study subjects.

Nasal Obstruction Severity Effectiveness (NOSE) Scale: A validated disease specific health status instrument to measure the outcome of subjects treated for nasal obstruction is a well-known and recognized validated 5-item instrument using a 5-point Likert Scale for patients with nasal obstruction. This outcome assessment has been used to measure improvements in QOL in septoplasty, functional septorhinoplasty and nasal valve surgery.

Visual Analog Scale (VAS) for Pain Intensity: The Pain VAS will be used to rate pain associated with the treatment (Hawker, Mian et al. 2011). Subjects will be asked to mark their pain level on a 10 cm line anchored by verbal descriptors: 0 = no pain and 10 = worst pain imaginable. The study staff will measure with a metric ruler from the 0, the beginning of the line, to the vertical mark made by the subject. The result, expressed in millimeters, will represent the subject's VAS Pain Score.

Adverse Event Evaluation: Subjects will be asked about any side effects or adverse experiences related to the Vivaer[®] treatment that they may have been experienced. All device related events will be documented on the proper Adverse Event Log and Adverse Event data form.

Medications: Updates to current medications or any new or changed medications will be asked. The medication log will be updated to reflect any changes. In addition, any medications as a result of intervention related to the study treatment will be documented and will correlate with the Adverse Event Case Report Form.

Quality of Life Questionnaire: Study-Specific Quality of Life (QOL) Questionnaire – The QOL questionnaire will be used to gain better understanding of the impact of nasal obstruction on the subject's daily activities, feelings, symptoms and medication use.

Table 1. Schedule of Assessments

Assessments	Prior to Nasal Valve Treatment	Nasal Valve, Treatment	Investigator Visual Assessment & subject follow-up at 3 months (+/- 2 weeks)	6, 12, 24 and 36 month Follow-ups (+/- 1 month)
Demographics and Medical History	X			
Nasal Evaluation	X	X	X	
Medication Review	X	X	X	X
Visual Assessment of Treatment Area & Photographs/videos	X	X	X	
Vivaer ARC Stylus Treatment		X		
NOSE Score	X		X	X
Visual Analog Scale (VAS)			X	
Subject QOL Questionnaire			X	X
Adverse Event Review		X	X	X
Study Exit				X*

*At 36 month visit

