10.0 ADVERSE EVENTS AND PRODUCT COMPLAINTS

10.1 Adverse Events

Adverse events (AEs) may occur during the treatment phase or during the follow-up phase. Adverse events occurring after the baseline assessment but before the treatment procedure will be documented in the subject's medical record but will not count as related to the study device or procedure.

Each adverse event will be recorded in the corresponding subject's CRF. Each adverse event will be judged by the Investigator as to its relationship and level of relatedness to the study device and/or study procedure. In addition, the Investigator will identify the date of onset, severity and duration of the AE. All adverse events will be monitored until they are adequately resolved or explained. If a subject reaches the 36 month follow-up visit and is experiencing a new or ongoing adverse event, the study sponsor should be contacted to discuss the need and/or methods for continued surveillance of the event.

The Investigator must submit to the Sponsor a report of any Serious Adverse Event (SAE), Serious Adverse Device Effect (SADE) or Unanticipated Adverse Device Effect (UADE) within 24 hours of knowledge of the event.

Sponsor Contact: [name], MSN, MPH
[contact]
Email: [contact]

In addition, the Investigator will report adverse events to the reviewing IRB / EC (as applicable) according to the local reporting requirements.

Adverse Events

Adverse Event (AE) – any untoward medical occurrence in a subject (ISO 14155).

NOTE: This definition does not imply that there is a relationship between the adverse event and the device under investigation.

Serious Adverse Event (SAE) – an adverse event that (ISO 14155):

- led to a death,
- led to a serious deterioration in the health of the subject,
- resulted in a life-threatening illness or injury,
- resulted in a permanent impairment of a body structure or a body function,
- required hospitalization or prolongation of existing hospitalization,
- resulted in medical or surgical intervention to prevent permanent impairment to body structure or function,
- led to fetal distress, fetal death, a congenital abnormality, or birth defect.

Adverse Device Effect (ADE) – any untoward and unintended response to a medical device (ISO 14155)

NOTE: This includes any event resulting from insufficiencies or inadequacies in the instructions for use or the deployment of the device. This definition also includes any event that is a result of user error.

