8.6 Adverse Events

Participants are queried about any side effects or adverse experiences related to the Vivaer procedure that they may have experienced. Incidence (type, severity, relatedness) of adverse events overall and by follow-up interval were recorded according to definitions provided in the study protocol.

9 STATISTICAL ANALYSIS**9.1 Analysis Populations****Full Analysis Set (FAS):**

The FAS is comprised of all enrolled participants that underwent the study procedure and met eligibility criteria.

Per-Protocol Eligible Set (PPS):

The PPS is comprised of all participants who met enrollment eligibility criteria, underwent the study and no major protocol deviations.

Safety Analysis Set:

The safety analysis population is comprised of all enrolled participants that have received any study-specific procedure, including screening procedures (eg, nasal endoscopy) and any part of the Vivaer procedure, including anesthesia.

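### The participant adverse-event question is worded as treatment-related, narrower than the all-event recording and reporting that the plan sets out elsewhere

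*Protocol*

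**What the plan says.** **Narrow text.** Protocol 9.6, under the adverse event evaluation, reads "Subjects will be asked about any side effects or adverse experiences related to the" Vivaer treatment. The next sentence covers documentation: "All device related events will be documented on the proper Adverse Event Log and Adverse Event data form". SAP 8.6 opens the same way: "Participants are queried about any side effects or adverse experiences related to the Vivaer procedure that they may have experienced".

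**Wide text.**
- Protocol 10.1 says "Each adverse event will be recorded in the corresponding" subject's CRF. A note to its AE definition adds: "This definition does not imply that there is a relationship between the adverse event and the device under investigation". On causality it says: "Each adverse event will be judged by the Investigator as to its relationship and level of relatedness to the study device and/or study procedure".
- Protocol 9.3 calls for evaluation of any AE at the 3-month visit.
- The synopsis lists the type and frequency of AEs through follow-up among its evaluations.
- SAP Table 1 makes AE incidence a safety measure, in total and per interval, with relatedness as one attribute.
- SAP 9.10 analyses all AEs in all participants and presents a time course.

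**Mixed text.** The second sentence of SAP 8.6 takes the wide scope: "adverse events overall and by follow-up interval were recorded according to definitions provided in the study protocol". So SAP 8.6 is not consistent within itself.

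**The concern.** In Protocol 10.1 and in the SAP tables, relatedness is a property that the Investigator assigns to an event already recorded. In the participant question it is a condition of entry, judged by the participant. Staff working from 9.6 and staff working from 10.1 could ask different questions and log different events, and SAP 9.3 pools their data.

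What is at stake is whether tables presented as all AEs rest on all-AE ascertainment. SAP section 2 allows the results to go into regulatory submissions, study reports and manuscripts, where a reader would take an all-AE table at face value.

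**Working it through.** The plan states no figure on this point and no arithmetic settles it. The check sets the passages side by side.

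1. **What is asked.** Protocol 9.6 and the first sentence of SAP 8.6 give the only wording of a question to participants about adverse events. Both tie it to the treatment or procedure.

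2. **What is logged.** Protocol 9.6 sends device-related events to the AE log and form. Protocol 10.1 sends every event to the CRF. The two can be followed together, because 9.6 does not restrict the log to device-related events. Even so, 9.6 names fewer events than 10.1. It does not name procedure-related events, which SAP Table 1 reports separately.

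3. **Who judges cause.** Under 10.1 it is the Investigator, event by event. Under the 9.6 question the participant judges first.

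4. **Does 10.1 remove the conflict?** Only in part. It governs an event once the site knows of it and does not say how the site is to find out. For a non-serious event with no other trace, the question is the main way the site finds out. The conflict therefore lies in the question more than in the log sentence.

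5. **Where it could matter.** The 3-month visit is in clinic, with physical and endoscopic examination and the broader instruction in 9.3. SAP section 3 describes the 6-, 12-, 24- and 36-month contacts as remote, by phone, and Protocol 9.4 lists questionnaires without an AE item. Protocol Table 1 does schedule an AE review at those contacts, with no limit to related events, but does not say what is asked.

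6. **Is the later review scheduled at all?** Protocol 9.6 opens: "The following study assessments will be collected at the specific time-points mentioned in the above phases". Since 9.4 does not mention AEs, that sentence and Table 1 do not match. But the phase lists are not exhaustive: 9.2 and 9.3 also leave out the medication review that Table 1 schedules. Table 1 is the better guide, and the gap in 9.4 is one of wording.

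7. **Other routes to an unattributed event.** At every follow-up the medication review asks about new or changed medicines with no causal condition. Part 4 of the quality-of-life questionnaire (SAP 8.4) asks about general health, including significant changes and further nasal surgery. Protocol 9.4 tells participants to contact staff about changes in health, medication or nasal procedures. These routes are real but indirect, and none is a standard AE question.

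8. **Size.** For an interval with N non-serious events that participants do not attribute to Vivaer, of which a share p reaches the site by any route, the under-count is N × (1 − p). The documents give neither N nor p. With p anywhere from 0 to 1, the result runs from N events missed to none, and nothing in the text narrows that range.

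**The case against.** The strongest reply is that nothing in 9.6 excludes unrelated events. It does not say only, 10.1 expressly covers the follow-up phase, and Table 1 schedules an unqualified AE review at every follow-up. Together with the medication review and the general-health items, a careful site would capture most of what matters. The study also has no hypothesis test, and the actual wording sits in an AE form that is not part of these documents.

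Most of this stands, and it is why the point is minor. It does not remove the mismatch: the only question wording the plan supplies is the narrow one, and it appears in both documents.

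Four stronger readings are tempting and are not supported:

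- **That unrelated AEs are not collected after 3 months.** A reader might count four of the five follow-up contacts, or 33 of 36 months, as uncovered. That count lets the broad wording of 9.3 override 9.6 at 3 months while giving no weight to the equally broad AE review in Table 1 later. It is also calendar time and not a measure of missed events, and participants who decline the extension leave at 24 months.
- **That the pivotal trial gives the size.** Protocol 5.0 reports 36 AEs there, none device-related and 13 procedure-related, which leaves 36 − 13 − 0 = 23 (23/36 = 64%). Most of the 36 events fell within 4 weeks of the procedure, in a different trial whose AE question is not described. The figure says nothing about months 6 to 36 here.
- **That the AE review is skipped at 6 to 36 months** because 9.4 omits it. Step 6 shows why this does not follow.
- **That the 3-month endpoint of device- and procedure-related serious AEs is compromised.** Events that participants attribute to treatment fall inside the question, the 3-month visit includes examination and the broader instruction, and 10.1 has a separate 24-hour route for serious events. The documents give no ground for this inference.

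**Conclusion.** The inconsistency is real and minor. Protocol 9.6 and the first sentence of SAP 8.6 solicit AEs more narrowly than Protocol 10.1 records them and than SAP Table 1 and SAP 9.10 report them. If the question was or is asked as worded, non-serious events that the participant does not link to Vivaer may be under-counted, most plausibly at the remote 6- to 36-month contacts.

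This rests on one assumption that the documents cannot confirm: that the form or question in use follows the 9.6 wording. If it already asks about any AE, only the text needs correcting. The size cannot be estimated, and the offsets listed above reduce it by an unknown amount. The consequence is limited to descriptive safety reporting; effectiveness results are not touched.

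**What to change.** 1. Reword Protocol 9.6 and the first sentence of SAP 8.6 so that participants are asked about any AE since the last contact. Log every event, whether device-related, procedure-related or neither, and have the Investigator assign relatedness afterwards, as 10.1 already requires.
2. List the AE review in Protocol 9.4 to match Protocol Table 1, as a wording alignment.
3. Check the wording of the AE form, or of whatever follow-up question was actually used. SAP section 3 indicates that some follow-up has already taken place, and rewording cannot recover those intervals.
4. For any interval collected with the related-only question, footnote the SAP 9.10 tables to say that the incidence of unrelated AEs may be incomplete.

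The cost is small: a few sentences in two documents, one check of the form, possibly a footnote, and a few more unrelated events for sites to enter and Investigators to judge.

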10.0 ADVERSE EVENTS AND PRODUCT COMPLAINTS

10.1 Adverse Events

Adverse events (AEs) may occur during the treatment phase or during the follow-up phase. Adverse events occurring after the baseline assessment but before the treatment procedure will be documented in the subject's medical record but will not count as related to the study device or procedure.

Each adverse event will be recorded in the corresponding subject's CRF. Each adverse event will be judged by the Investigator as to its relationship and level of relatedness to the study device and/or study procedure. In addition, the Investigator will identify the date of onset, severity and duration of the AE. All adverse events will be monitored until they are adequately resolved or explained. If a subject reaches the 36 month follow-up visit and is experiencing a new or ongoing adverse event, the study sponsor should be contacted to discuss the need and/or methods for continued surveillance of the event.

The Investigator must submit to the Sponsor a report of any Serious Adverse Event (SAE), Serious Adverse Device Effect (SADE) or Unanticipated Adverse Device Effect (UADE) within 24 hours of knowledge of the event.

Sponsor Contact: [name], MSN, MPH
[contact]
Email: [contact]

In addition, the Investigator will report adverse events to the reviewing IRB / EC (as applicable) according to the local reporting requirements.

Adverse Events

Adverse Event (AE) – any untoward medical occurrence in a subject (ISO 14155).

NOTE: This definition does not imply that there is a relationship between the adverse event and the device under investigation.

Serious Adverse Event (SAE) – an adverse event that (ISO 14155):

- led to a death,
- led to a serious deterioration in the health of the subject,
- resulted in a life-threatening illness or injury,
- resulted in a permanent impairment of a body structure or a body function,
- required hospitalization or prolongation of existing hospitalization,
- resulted in medical or surgical intervention to prevent permanent impairment to body structure or function,
- led to fetal distress, fetal death, a congenital abnormality, or birth defect.

Adverse Device Effect (ADE) – any untoward and unintended response to a medical device (ISO 14155)

NOTE: This includes any event resulting from insufficiencies or inadequacies in the instructions for use or the deployment of the device. This definition also includes any event that is a result of user error.

Serious Adverse Device Effect (SADE) – an adverse device effect that has resulted in any of the consequences characteristic of a serious adverse event or that might have led to any of these consequences if suitable action had not been taken or intervention had not been made or if circumstances had been less opportune (ISO 14155).

Anticipated Adverse Device Effect (AADE) – an adverse device effect which by its nature, incidence, severity or outcome has been previously identified in the previously identified in nature, severity, or degree of incidence in the investigational plan or application

Unanticipated Adverse Device Effect (UADE) – any serious adverse effect on health or safety or any life-threatening problem or death caused by, or associated with, a device, if that effect, problem, or death was not previously identified in nature, severity, or degree of incidence in the investigational plan or application (including a supplementary plan or application), or any other unanticipated serious problem associated with a device that relates to the rights, safety, or welfare of subjects (21 CFR 812.3(s) and ISO 14155).

NOTE: The occurrence of a diagnostic or elective surgical procedure for a pre-existing condition, unless the condition becomes more severe or increases in frequency, would not be considered procedure or device-related.

10.2 Product Complaints

Product Complaint - Any written, electronic or oral communication that alleges deficiencies related to the identity, quality, durability, reliability, safety, effectiveness, or performance of an Aerin product (medical device) after it is released for distribution [per 21 CFR 820.3(b)].

Complaint – written, electronic or oral communication that alleges deficiencies related to the identity, quality, durability, reliability, usability, safety or performance of a medical device that has been released from the organization's control or related to a service that affects the performance of such medical device [per ISO 13485:2016].

Reportable Complaint – Any product complaint that represents an event, which must be reported to a regulatory agency including:

- US Food and Drug Administration (per 21 CFR Part 803)
- A Competent Authority within the European Community or a Notified Body (MDD)
- The Canadian HPFB
- Any regulatory agency, within the country of distribution.

11.0 SUBJECT REIMBURSEMENT

Subjects will be reimbursed for their time for completing questionnaires as allowed by the IRB and study site policies. Subjects will not be reimbursed for questionnaires not completed.

12.0 RISK-BENEFITS

12.1 Potential Risks to Patient Confidentiality

Risks to patient confidentiality are minimized by only allowing authorized individuals to access the EDC system, which is 21 CFR Part 11 compliant. The validated system maintains an audit trail on all entries, changes or corrections to eCRFs. If a person only authorized to complete eCRFs makes changes to an already signed eCRF, the investigator will be required to resign the eCRF, thereby protecting the integrity of the data collection process and the data.

The electronically driven subject reported questionnaire system enables subject privacy protection and full data attribution through the use of a unique username, password and provides a full audit trail. The system employs Advanced Encryption Standard (AES) for data in transit, at rest and in system backups. The data collection process uses encryption with, at least, 256-bit Secure Sockets Layer (SSL) and 2048 bit RSA public keys while providing the subject a user-friendly method to provide patient reported outcomes (PRO)'s.

12.2 Minimization of Anticipated Risks

Risks associated with the Vivaer[®] ARC Stylus are minimized by design. In addition, risks will be minimized through the use of a treating physician with a high degree of experience in nasal surgical and minimally invasive procedures. The treating physician will have received new customer training in proper use of the device prior to study start.

12.3 Potential Benefits

Potential benefit, associated with the Vivaer[®] treatment, is to offer a safe, minimally invasive treatment method to alleviate the symptoms of nasal obstruction. The Vivaer[®] ARC Stylus improves nasal breathing by modifying the tissues of the nasal airway using low doses of radiofrequency energy. The low-power radiofrequency energy generates heat within the tissue and creates a coagulation lesion. As the lesion heals, the tissue retracts and stiffens, thereby decreasing nasal airway obstruction and improving airflow.

13.0 STUDY MANAGEMENT

This study will be conducted in accordance with elements of E6 Good Clinical Practice Consolidated Guidance, ICH, April 1996, Abbreviated Requirements of 21 CFR 812 for NSR device studies, the Declaration of Helsinki, the Belmont Report and any conditions imposed by the reviewing IRB or US FDA or other regulatory agency.

The study sponsor has the overall responsibility for the conduct of the study according to all applicable regulatory requirements. The study sponsor will have certain direct responsibilities and will delegate other responsibilities to the treating physician. The study sponsor and treating physician will ensure that the study is conducted according to all applicable regulations. All personnel to participate in the conduct of this clinical trial will be qualified by education and / or experience to perform their tasks.

The study sponsor, treating physician or any person acting for or on behalf of a sponsor or treating physician shall act in accordance the applicable standards, guidelines and regulations.

